#### 5.5.1 Lost-to-Follow-up

If the subject misses two consecutive scheduled follow-up visits and the attempts at contacting the subject detailed below are unsuccessful, then the subject is considered lost-to-follow-up. Site personnel shall make all reasonable efforts to locate and communicate with the subject (and document these efforts in the source documents), including the following, at each contact time point:

- A minimum of two telephone calls on different days over the specified follow-up windows to contact the subject should be recorded in the source documentation, including date, time and initials of site personnel trying to make contact.
- If these attempts are unsuccessful, a certified or registered letter should be sent to the subject.
- If a subject misses one or more non-consecutive follow-up contact time points, it will be considered a missed visit. The subject may then return for subsequent visits. If the subject misses two consecutive time points and the above-mentioned attempts at communicating with the subject are unsuccessful, the subject will be considered lost-to-follow-up.

**Note:** Telephone contact with General Practitioner, non-clinical study cardiologist or relative will be considered as subject contact for the purpose of collecting vital status information. The center shall retain records of the contact.

### 5.6 Number of Subjects

A total of 169 analysis subjects (up to a total of 189 subjects including roll-ins) will undergo an attempted Navitor implant in order to analyze the primary endpoints for the Portico NG cohort. Furthermore, a total of 60 analysis subjects will undergo an attempted Navitor Titan implant for the PMA submission. To ensure

## Clinical Investigation Plan

enrollment balance across study sites, no site may enroll more than 20% of the analysis population (n=33 for the Portico NG cohort and n=12 for the Titan cohort).

### 5.7 Duration of the Clinical Study

The expected duration of each subject's participation in the clinical study is 5 years, including the scheduled visits and data collection as listed in Section 6.5.5. All enrolled subjects will be followed until their 5-year visit, subject withdrawal, or study closure, whichever occurs first. Subjects that are exited from the study after providing Informed Consent but prior to enrollment in the study will not require any additional follow-up.

Overall, the total duration of the clinical study is expected to be approximately [REDACTED] years, based on an expected enrollment period of 12 months, 5 years of follow-up for each subject, and approximately 6 months for study closure activities and results reporting.

## 6 TREATMENT AND EVALUATION OF ENDPOINTS

### 6.1 Baseline

For subjects that have successfully completed screening, scheduled visits will be performed in the following order: Baseline, Index Procedure, Discharge, 30 days, 12 months, and annual follow-up assessments to 5 years.

#### 6.1.1 Baseline Assessments

Subjects who are deemed eligible for implantation of a Navitor Valve using the FlexNav Delivery System will undergo a baseline visit prior to the procedure (may occur on the day of, procedure prior to the implant procedure).

The following baseline assessments will be performed for all subjects prior to the index procedure.

1. Chest X-ray (if standard of care)
2. Cardiovascular medications documentation (including dosage)
3. Modified Rankin Scale (mRS)
4. NIH Stroke Scale (NIHSS)
5. Barthel Index
6. Quality of Life Measures (SF-36)
7. Mini Mental State Exam (MMSE-2:SV)
8. Six Minute Walk Test (6MWT)
9. Lab Measurements (Troponin or CK/CK-MB, INR if subject is on Coumadin or Warfarin or other anticoagulants/vitamin K antagonists in lieu of warfarin)
10. Adverse events assessment

Excluding the chest X-ray scan which is standard of care and will be conducted per hospital guidelines, all baseline assessments are considered study-related assessments.

## Clinical Investigation Plan

### 6.1.2 Pre-procedure Antiplatelet/Anticoagulant Medications

Antiplatelet/Anticoagulation and other medications should be administered pre-procedure per the standard of care at the investigational site.

### 6.1.3 Pre-procedure Blood Tests

The following blood tests will be performed at the investigational site within 72 hours prior to the index procedure:

1. Cardiac enzymes (Troponin or CK/CK-MB)
2. BUN and Creatinine

## 6.2 Index Procedure

### 6.2.1 Procedures Involved in the Use of the Device Under Investigation

Please refer to IFU for instructions on handling and preparation of the Navitor Valve, FlexNav Delivery System, Navitor Loading System. All Investigators must read and understand the IFU and Investigator Brochure, as applicable.

### 6.2.2 Procedural Anticoagulation

Anticoagulation use during the procedure is left to the physician's discretion or should be established as with any other transcatheter valve implantation, considering risks and benefits for the patient. The activated clotting time (ACT) should be monitored and recorded on source documentation during the procedure and medications should be adjusted to attempt to keep the subject's ACT > 250 seconds.

### 6.2.3 Implant Procedure

It is recommended (required for US sites per the Medicare National Coverage Decision) that the heart team's interventional cardiologist(s) and cardiac surgeon(s) jointly participate in the intra-operative technical aspects of the TAVR procedure.

It is strongly recommended that the index procedure occur within 14 calendar days following SSC approval.

A Navitor Valve may be implanted in a subject who has signed the ICF and Data Protection Form (if applicable) and approved by the SSC. Although not recommended, if a physician determines it is in the best interest of the subject to have a second transcatheter aortic valve placed, a subject may receive an additional transcatheter aortic valve.

Standardized imaging techniques will be used during the index procedure to implant the valve and to assess valve performance and coronary patency.

The following data will be collected during the implant procedure:

1. Device access, deployment and final valve placement data collection
2. Aortic systolic/diastolic pressure, mean aortic pressure, mean aortic valve gradient, peak aortic valve gradient and aortic regurgitation (post-implant only) immediately pre- and post implant,
3. If performed, right atrial pressure, pulmonary artery systolic/diastolic pressure, mean pulmonary artery pressure, pulmonary capillary wedge pressure (PCWP) immediately pre- and post implant
4. Cardiac rhythm monitoring and rhythm changes throughout the duration of the procedure

## Clinical Investigation Plan

5. Procedural information and imaging (angiogram, cine, intra-procedure echocardiography to be available to the Sponsor and provided upon request by the site)

Investigational sites should follow study-specific guidelines for the assessment of aortic regurgitation and implant depth. Refer to APPENDIX XIII for a description of standardized methods for measuring aortic regurgitation according to VARC-2 criteria and instructions for assessing implant depth in the LVOT.

During the procedure, the implanting physician may determine implantation of the Navitor valve is either not feasible or not in the best interest of the patient. Reasons may include, but are not limited to, anatomy that is not suitable for implantation, inability to gain access, ventricular arrhythmia, or any other contraindication. If the implant procedure was not attempted (i.e., the FlexNav Delivery System was never introduced into the subject's vasculature), the subject will be considered a procedural exclusion.

If the implant procedure was attempted (i.e. the FlexNav Delivery System was introduced into subject's vasculature) but the Navitor Valve could not be implanted (e.g. Navitor attempted but other valve ultimately placed in the annulus), the subject will be withdrawn from the study after a 30-day adverse event collection period.

All the required information must be recorded on the applicable CRF. Following the procedure, the FlexNav Delivery System and Navitor Loading System should be securely disposed as per hospital requirements for hazardous materials. If there are any concerns noted with the Navitor Valve, FlexNav Delivery System, or the Navitor Loading System during the procedure, these products should be returned to the Sponsor for evaluation.

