### 4.3 Descriptive Endpoints

The following key outcomes (relevant to characterizing the safety profile and outcomes based on the design modifications) will be assessed as descriptive endpoints for the study (for both the Portico NG and Titan cohorts, but analyzed independently for each cohort):

- Technical device success defined as successful vascular access, delivery and deployment of the Navitor Valve; retrieval with the delivery system and correct positioning of a single valve in the proper anatomical location and the absence of procedural mortality
- All-cause mortality at 12 months from the index procedure
- Cardiovascular-related mortality at 30 days and 12 months from the index procedure
- Disabling stroke at 30 days and 12 months from the index procedure
- Life threatening and major bleeding at 30 days from the index procedure
- Acute kidney injury at 30 days from the index procedure
- Major and minor vascular complications at 30 days from the index procedure
- Permanent pacemaker insertion at 30 days and 12 months from the index procedure
- Changes in functional status from baseline to follow-up assessments at 30 days and 12 months (e.g., NYHA classification, six-minute walk test, quality of life measures)
- Paravalvular leak at discharge, 30 days and 12 months from the index procedure
- Changes in echocardiographic parameters from baseline to follow-up at 30 days and 12 months (e.g., mean effective orifice area, mean transvalvular gradient, mean peak velocity)
- Symptomatic valve thrombosis at 30 days and 12 months from the index procedure

Additional outcomes to be collected and assessed during the study:

- Myocardial infarction at 30 days and 12 months from the index procedure
- New-onset atrial fibrillation at 30 days and 12 months from the index procedure
- Coronary obstruction requiring intervention at 30 days from the index procedure
- Valve embolization during procedure, and at 30 days and 12 months from the index procedure
- Reintervention to treat valve-related dysfunction at 30 days and 12 months from the index procedure
- Total aortic valve regurgitation (transvalvular plus paravalvular leak) at discharge, 30 days and 12 months from the index procedure

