## Clinical Investigation Plan

### 5.4 Subject Enrollment

The point of a subject's enrollment in the clinical study is completion of signing the informed consent.

Consented subjects who undergo study-specific testing and are found to have met exclusion criteria or not all inclusion criteria (or if a site disagrees with the Subject Selection Committee's decision regarding risk classification) will be considered screen failures; these subjects will not be counted toward the sample size of 169 analysis subjects and will be exited from the study without further follow-up.

In addition, consented subjects who undergo study-specific testing and meet study criteria but do not undergo a Navitor implant attempt (defined as insertion of the delivery system into the vasculature) will not be counted toward the sample size of 169 analysis subjects and will be exited from the study without further follow up.

All subjects who undergo a Navitor implant attempt will be included in the analysis population or designated as roll-in as described in Section 5.4.1. Subjects who undergo a Navitor implant attempt but are not implanted with the Navitor Valve will be followed for 30 days and then exited from the study; similarly, any subject who undergoes explant of the Navitor Valve during the study follow-up period will be exited from the study 30 days following the explant procedure.

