### 8.1 Analysis Population

The analysis population will include all subjects in whom a Navitor implant is attempted, excluding roll-in cases. A Navitor implant attempt is defined as insertion of the FlexNav Delivery System (loaded with a Navitor Valve) into the subject's vasculature.

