## 2.0 **ANALYSIS CONSIDERATIONS**

### 2.1 **Analysis Populations**

#### 2.1.1 **Attempted Population**

The attempted population will include all subjects in whom a Navitor implant is attempted, excluding roll-in cases. A Navitor implant attempt is defined as insertion of the FlexNav™ Delivery System (loaded with a Navitor valve) into the subject's vasculature.

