### 2.3.3 Descriptive Endpoints

Hemodynamic outcomes such as mean gradient, effective orifice area (EOA), paravalvular leak, etc. will be analyzed in the Implanted population described in Section 2.1.2, other descriptive endpoints will be analyzed in the Attempted population described in Section 2.1.1. All analyses will be performed on available data.

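### Technical device success requires vascular access but is scored only after FlexNav is inserted, so procedures abandoned before insertion cannot count as failures and their outcomes reach no planned safety analysis

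*Protocol*

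**What the plan says.** Protocol 4.3 gives the endpoint: "Technical device success defined as successful vascular access, delivery and deployment of the Navitor Valve", followed by retrieval, correct positioning of a single valve and no procedural death. SAP 1.4.4 repeats it.

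SAP 2.3.3 assigns hemodynamic outcomes to the Implanted population and says that "other descriptive endpoints will be analyzed in the Attempted population described in Section 2.1.1". Technical success falls in that second group. SAP 2.1.1 sets the entry point: "A Navitor implant attempt is defined as insertion of the FlexNav™ Delivery System (loaded with a Navitor valve) into the subject's vasculature". The protocol agrees in section 8.1: "The analysis population will include all subjects in whom a Navitor implant is attempted, excluding roll-in cases".

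Protocol 6.2.3 covers decisions taken during the procedure. Its reasons for not implanting are "anatomy that is not suitable for implantation, inability to gain access, ventricular arrhythmia, or any other contraindication". Where "the FlexNav Delivery System was never introduced into the subject's vasculature), the subject will be considered a procedural exclusion", the subject never reaches the Attempted population.

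Protocol 5.4 says that screen failures "will not be counted toward the sample size of 169 analysis subjects and will be exited from the study without further follow-up", and repeats that disposition for eligible, consented subjects who "do not undergo a Navitor implant attempt (defined as insertion of the delivery system into the vasculature"). By contrast, sections 5.4, 6.2.3 and 6.5.2 keep a subject whose FlexNav was inserted but who received no Navitor valve in the analysis and follow that subject for 30 days.

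**The concern.** The endpoint's definition and its denominator do not fit together. The definition asks whether access succeeded, while the denominator admits only subjects in whom the delivery system is already inside a vessel. The protocol itself foresees failure to gain access, so this is an expected outcome that the plan removes before scoring.

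The same filter affects safety reporting. Two subjects may both have undergone the study's index procedure. The one stopped just after FlexNav insertion gets 30-day follow-up and a place in every safety table. The one stopped just before gets neither. If the second subject has an event, leaving it out favours the device. A reader of the final report could not tell whether these exclusions were harmless.

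**Working it through.** The plan states no figure that depends on this point, so there is nothing to reproduce. The check traces each endpoint to its population and then shows scale under stated assumptions.

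**Step 1. Does a subject abandoned before insertion appear?**

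| Analysis | Population | Appears? |
|---|---|---|
| Technical success (SAP 2.3.3) | Attempted | No |
| 30-day mortality, both cohorts (SAP 2.3.1.1, 2.3.1.2) | Attempted | No |
| Secondary composite (SAP 2.3.2) | Attempted | No |
| General AE, SAE and adjudicated-event tables (SAP 3.2) | Attempted | No |
| Sensitivity analyses (SAP 2.13) | About COVID-19 relatedness only | No set from procedure start |
| Early termination, including deaths (SAP 3.3) | Not restricted to Attempted | Possibly |

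**Step 2. What is collected?** Safety reporting begins at enrollment, which is consent, and ends when participation ends (Protocol 5.4, 7.3.1). CRF data cover all consented subjects (11.4). An event before exit is therefore reportable; an event after exit is not collected.

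**Step 3. Number of subjects.** The documents give no rate of abandonment before insertion. I assume 1%, 2% and 3% of the attempts.
- Portico NG, 169 attempts (Protocol 8.3): 0.01 × 169 = 1.7; 0.02 × 169 = 3.4; 0.03 × 169 = 5.1. About 2-5 subjects.
- Titan, 60 attempts: 0.6, 1.2 and 1.8. About 1-2 subjects.

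**Step 4. Effect on technical success.** With x successes among n attempts and k access failures before insertion, the reported rate is x/n and the rate from procedure start is x/(n + k). The largest possible gap, reached when x = n, is k/(n + k).
- Portico NG: k = 2 gives 2/171 = 1.2 points; k = 3 gives 3/172 = 1.7; k = 5 gives 5/174 = 2.9.
- Titan: k = 1 gives 1/61 = 1.6 points; k = 2 gives 2/62 = 3.2.

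**Step 5. The access component alone.** Suppose no attempted subject is scored as an access failure. Exact (Clopper-Pearson) 95% limits:
- Portico NG: 0/169, upper limit 2.2%. With three excluded failures restored, 3/172 = 1.7% (0.4% to 5.0%).
- Titan: 0/60, upper limit 6.0%. With one restored, 1/61 = 1.6% (0.0% to 8.8%).

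**Step 6. Mortality, illustration only.** With assumed counts, 4/169 = 2.4% (0.6% to 5.9%) becomes 5/170 = 2.9% (1.0% to 6.7%) if one excluded subject died.

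**The case against.** The strongest reply is that an attempted-implant population is a legitimate choice. Its trigger is objective, the protocol and SAP define it in the same way, and safety is compared only descriptively with published device studies, whose own starting point these documents do not show. CT core laboratory review of the access route, committee approval and the vessel exclusion criteria should also make abandonment for access uncommon. All of this stands, and it is why the primary populations should not change. It does not rescue technical success, because there the plan itself names access as part of what is being measured.

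Three stronger readings are tempting, and the documents do not support them.
- *All early access deaths and injuries leave the safety endpoints.* Only events in subjects who never have FlexNav inserted leave. An access injury followed by insertion is counted. So is one caused by FlexNav's own entry, since its integrated sheath can serve as the introducer (Protocol 15.5).
- *Technical success cannot fail, or is uninformative.* FlexNav may enter and fail to advance, and delivery, deployment, retrieval, positioning and procedural death are all still scored.
- *Harm in these subjects goes unrecorded.* Events before exit are reportable: serious events go to the sponsor within 3 calendar days (7.3.1), and deaths may be listed under SAP 3.3. What is missing is collection after exit and any endpoint analysis.

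**Conclusion.** The point holds in limited form. As written, access failures before insertion cannot count against technical success, so the reported rate is biased upward relative to the endpoint's own definition. The size cannot be estimated from the documents. If 1-3% of procedures are abandoned before insertion, all for failed access, the gap is at most about 1-3 percentage points in either cohort. Separately, deaths, vascular injuries and bleeds in never-inserted subjects are absent from 30-day mortality, the secondary composite and the general AE tables, and their events after exit are unknown.

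Technical success is descriptive and is in no success criterion. A reader might infer that the Titan decision is at risk, since three deaths pass and a fourth, before insertion, would go uncounted. The documents do not support a change there: Protocol 8.11 counts deaths among 60 analysis subjects, such a subject is not one of them, and nothing proposed here alters that rule. The case for acting is that the change costs little and removes an omission that can only favour the device.

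**What to change.** 1. **Protocol 5.4 and 6.2.3.** For subjects in whom arterial access for a planned Navitor implant was begun but FlexNav was not inserted, collect adverse events and vital status to 30 days, as is already done for attempted-but-not-implanted subjects.
2. **SAP 2.1.** Add a 'procedure started' set: the Attempted population plus these subjects, still excluding roll-ins.
3. **SAP 2.3.3.** Compute technical device success in that set, and show the Attempted-population result beside it.
4. **Supplementary table.** Report the number of procedural exclusions and their reasons, and give 30-day mortality and the secondary composite in the 'procedure started' set.
5. **Unchanged.** The primary analysis populations and the Titan success rule.

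If the sponsor prefers not to add the set, the least it should do is state that access success is conditional on FlexNav insertion and tabulate the number, reasons and known events of the procedural exclusions.

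The cost is brief follow-up of probably a few subjects, one extra table, and possibly a slightly lower reported technical success rate.

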### 6.2.4 Post-procedure Imaging

Subjects implanted with a Navitor Valve will be required to undergo an echocardiogram between 24 and 48 hours after the procedure.

## 6.3 Post-procedure (In-hospital)

### 6.3.1 Post-procedure Laboratory Tests

The following laboratory tests should be performed in-hospital post-implant procedure:

1. Troponin, or CK / CK-MB should be collected between approximately 12 and 24 hours after procedure, between approximately 36 and 48 hours after the procedure, and at approximately 72 hours after the procedure (or at discharge, if patient is discharged prior to 72 hours post procedure).
2. BUN and Creatinine to be collected within 72 hours after index procedure

## 6.4 Discharge Assessments

The discharge visit will take place at the time of hospital discharge or at 7 days after the procedure, whichever occurs first. If the subject is expected to be discharged over the weekend, the discharge tests may be completed on the last week day prior to discharge.

The discharge assessment will include:

1. Physical exam (weight, heart rate, blood pressure)
2. Modified Rankin Scale (mRS)
3. NIH Stroke Scale (NIHSS)

## Clinical Investigation Plan

4. Barthel Index
5. Echocardiogram (if not performed during the post procedure testing within 48 hours after procedure)
6. 12 lead ECG (for subjects receiving a new permanent pacemaker, ECG should be completed showing the underlying rhythm as well as the current pacing programming)
7. Cardiovascular medications documentation
8. Adverse events assessment
9. Lab Measurements (CBC and Platelet count, BUN and Creatinine, and Troponin or CK/CK-MB if patient is discharged prior to 72 hours post-procedure)

### 6.5 Follow-up Assessments

#### 6.5.1 Follow-up Medications

Medications administered to subjects during the follow-up period will be at the physician's discretion.

## Clinical Investigation Plan

care (e.g., contrast CT scan or TEE) to evaluate device specific findings (e.g., valve thrombosis); if performed, this additional imaging will be sent to the Sponsor for analysis.

